5.3 Variables to be Measured to Demonstrate Achievement of Endpoints

To evaluate deployment characteristics, procedural outcome, and follow-up, the following data points will be collected:

- 1) Assessment of system performance including: deployment issues, ease of insertion, visualization, and ease of removal;
- 2) Clinical utility measures such as days to discharge from hospital;
- 3) Complications including major adverse events during procedure and at follow-up;
- 4) Device integrity findings at completion of procedure and follow-up: device migration, patency, stent fracture, and graft kinks;
- 5) Type and sources of endoleaks at procedure and follow-up; and
- 6) Secondary interventions performed.

5.4 Measures to be Taken to Avoid or Minimize Bias

This study is not randomized or blinded. It is intended to prospectively collect information regarding the safety and effectiveness of the Zenith® TX2® Low Profile Endovascular Graft. The study will utilize uniform definitions for study endpoints, event adjudication by an independent clinical events committee, and imaging data analysis by a centralized core laboratory. Study results will be analyzed in accordance with a prospectively defined analysis plan.

5.5 Study Criteria

Assessment of entry criteria will be based upon data available pre-operatively. Data obtained peri-operatively and post-operatively (including the results from core laboratory analysis of pre-procedure imaging) may contradict pre-operative assessment. However, such contradiction is not considered a violation of the Clinical Investigation Plan and should not be construed as evidence of inadequate or inaccurate pre-operative assessment with respect to the enrollment criteria or evidence of inappropriate enrollment. Enrollment is to be based upon best available pre-operative data. Some criteria relate to subjective assessment while other criteria are considered absolute and able to be determined definitively. Variability in assessment between centers, investigators, and observers is expected with several criteria.

5.5.1 Inclusion Criteria

All patients must meet all of the following inclusion criteria to be eligible for enrollment into this study:

- 1) Blunt thoracic aortic injury of the descending thoracic aorta
- 2) Suitable for treatment with the Zenith® TX2® Low Profile Endovascular Graft and 16 Fr, 18 Fr, or 20 Fr Z-Trak Plus® Introduction System
- 3) Treatment with the Zenith® TX2® Low Profile Endovascular Graft can be performed within 14 days of the blunt thoracic aortic injury
- 4) Age \geq 16 years
- 5) Proximal fixation site length measuring \geq 20 mm between the left common carotid artery and most proximal extent of the injury site (covering left subclavian artery is acceptable)
- 6) Distal fixation site length measuring \geq 20 mm between the distal-most aspect of aortic injury and most distal extent of graft
- 7) No previous placement of a thoracic endovascular graft
- 8) No prior open surgical repair involving the descending thoracic aorta including suprarenal aorta and/or arch
- 9) Proximal neck diameter, measured outer-wall to outer-wall on a sectional image or multiplanar reconstruction (CT), \geq 15 mm and \leq 42 mm
- 10) Distal neck diameter, measured outer-wall to outer-wall on a sectional image or multiplanar reconstruction (CT), \geq 15 mm and \leq 42 mm
- 11) Ability to preserve the left common carotid artery and celiac artery
- 12) Willing and able to comply with the follow-up schedule

- 13) Informed consent given by the patient or a legally authorized representative [Note: For pediatric patients, in addition to obtaining permission from their parents or guardians, assent from the patients may need to be obtained based on IRB requirements. See Section 6.2 for further information.]

5.5.2 Exclusion Criteria

Patients must be excluded if any of the following general, medical, or anatomical exclusion criteria are true:

General Exclusion Criteria

- 1) Injury severity score (see Appendix C, Definitions) at the time of initial hospital admission is 75
- 2) Aortic injuries classified as grade 1⁸ (see Appendix C, Definition of Traumatic Aortic Injury)

Medical Exclusion Criteria

- 1) Pregnancy
- 2) Known allergy to polyester, polypropylene, nitinol, or gold
- 3) Allergic reaction to contrast, which in the opinion of the investigator, cannot be adequately premedicated
- 4) Aortic dissection
- 5) Systemic infection (e.g., sepsis)
- 6) Degenerative connective tissue disorder (e.g., Marfan's disease)
- 7) Bleeding diathesis, uncorrectable coagulopathy, or refusal of blood transfusion
- 8) Simultaneously participating in another investigative device or drug study (The patient must have completed the primary endpoint of any previous study at least 30 days prior to enrollment in this study and not enroll in another study until 30 days after blunt thoracic aortic injury repair in this study)

Anatomical Exclusion Criteria

- 1) Treatment length (i.e., length of aortic injury including proximal and distal fixation sites) along greater curvature:
 - > 105 mm for 18 mm to 26 mm diameter grafts
 - > 109 mm for 28 mm to 32 mm diameter grafts
 - > 113 mm for 34 mm to 36 mm diameter grafts
 - > 117 mm for 38 mm to 40 mm diameter grafts
 - > 121 mm for 42 mm diameter grafts
 - > 125 mm for 44 mm to 46 mm diameter grafts
- 2) Aortic arch radius of curvature < 20 mm (only if the device is intended to be deployed in the aortic arch)
- 3) Tortuosity, calcification, occlusive disease, or arterial diameter of the intended access vessels (e.g., iliac and/or femoral arteries), measured inner-wall to inner-wall on a sectional image, that are not conducive to placement of the introducer sheath (16 Fr for 18 mm to 30 mm diameter grafts, 18 Fr for 32 mm to 38 mm diameter grafts, 20 Fr for 40 mm to 46 mm diameter grafts) – use of an access conduit is acceptable
- 4) Prohibitive calcification, occlusive disease, or tortuosity of intended fixation sites
- 5) Circumferential thrombus in region of intended fixation sites
- 6) Aneurysm or angulation in the distal thoracic aorta that would preclude advancement of the introduction system

5.6 Point of Enrollment

Point of enrollment will be based on the intent-to-treat population, and is defined to include any patient in whom the treatment procedure is initiated. More specifically, once a procedure has begun (i.e., cutdown or percutaneous access initiated), the patient will be included in the intent-to-treat population. The patient's informed consent will be obtained and assessment of the patient's conformance to the inclusion/exclusion criteria will occur prior to the procedure.

5.7 Enrollment Objective

Fifty patients will be enrolled to provide greater assurance of the study results and to also account for possible loss to follow-up or withdrawal from the study. Up to 30 centers in the US and outside the US may participate.

6.0 Methods

6.1 Subject Assessment and Screening

Patients will be screened prior to the procedure to ensure they meet all of the inclusion and none of the exclusion criteria.

6.2 Subject Consent

Patients who meet all of the inclusion and none of the exclusion criteria will be invited to participate in this investigation. All patients eligible for entry into the investigation will have the clinical investigation plan explained to them, as well as potential risks and benefits of their participation in the investigation.

Informed consent from the patient or a legally-authorized representative will be obtained (in accordance with 21 CFR 50) prior to the procedure or any study-specific testing.

A short-form consent document, in accordance with 21 CFR 50.27, may be developed, to allow for oral presentation of the elements of the informed consent to the patient. Because in many instances the patient may not be able to provide consent and the legally-authorized representative may not be able to be present at the hospital immediately, approval for telephone consent (wherein treatment options are discussed with the legally-authorized representative over the phone, and a consent form is then either faxed or emailed to the individual so the individual can sign and return the consent form via fax or email) may be sought from the IRBs/ECs (see Appendix D for short-form and telephone consent templates).

For pediatric patients, in addition to obtaining permission from the parents or guardians of the patient, assent from the patient may be necessary based on the requirements of the IRB.

Patients will not be treated with the Zenith® TX2® Low Profile Endovascular Graft in emergency situations where prior consent of the patient or the patient's legally-authorized representative in accordance with 21 CFR Part 50.24 is not possible.

This study will not be conducted as emergency research under 21 CFR 50.24. Use of study devices in an emergent situation, wherein a patient or a legally-authorized representative is unable to provide consent, must be reported according to applicable FDA and IRB/EC requirements.

6.3 Medications

The hospital's standard protocol should be followed with respect to medications.

6.4 Pre-procedure

Grafts are sized based on pre-operative radiologic findings, using computerized tomography (CT). Please reference the Instructions for Use for details regarding the suggested imaging studies to be obtained and sizing guidelines.

Because patients with traumatic aortic injury most often have other serious concomitant non-aortic injuries, endovascular repair of the aortic injury may be postponed until other injuries have been treated.

6.5 Procedure

Standard techniques for placement of arterial access sheaths, guiding catheters, angiographic catheters, and wire guides should be employed during use of the Zenith[®] TX2[®] Low Profile Endovascular Graft. The Zenith[®] TX2[®] Low Profile Endovascular Graft is compatible with 0.035 inch diameter wire guides.

Reference the institutional protocols and SVS guidelines relating to anesthesia, anticoagulation, access technique, spinal drainage, and monitoring of vital signs. Coverage of the left subclavian artery is acceptable; however, revascularization of the left subclavian artery should be considered.³

Reference the Instructions for Use for complete details regarding use of the Zenith[®] TX2[®] Low Profile Endovascular Graft. Fluoroscopic guidance and angiography should be used throughout the procedure to verify positioning of the device with respect to the patient's anatomy.

6.6 Peri-operative

Reference the institutional protocols for peri-operative management of patients undergoing treatment for BTAI.

6.7 Post-operative Treatment of Endoleaks

Type I and type III endoleaks warrant immediate treatment. Type II endoleaks should be treated at the physician’s discretion, depending on endoleak source and time from implantation. Type III endoleaks should be treated with additional ballooning or prostheses.

6.8 Secondary Interventions

Some patients may need secondary intervention(s) for treatment of endoleaks, device migration, etc. The timing and method of such interventions are based on the judgment of the treating physician. If ancillary devices (balloons, stents, etc.) are used during these interventions, it is recommended that Instructions for Use (IFU) of that device be reviewed, and the risks of using that device be considered.

6.9 Follow-up

The results of the endovascular repair will be assessed by clinical and/or imaging evaluation intra-operatively and post-operatively, including within 7 days post-procedure, at 30 days (± 10 days) post-procedure, and at 6 months (180 ± 30 days), 12 months (365 ± 45 days), 2 years (730 ± 60 days), 3 years (1095 ± 60 days), 4 years (1460 ± 90 days), and 5 years (1825 ± 90 days) post-procedure as summarized in Table 2. Follow-up windows are intended as guidelines only. They are not absolute and are not intended to limit data collection due to scheduling conflicts.

Table 2. Study follow-up schedule

	Pre-op	Intra-op	Post-procedure	30-day	6-month	12-month ³
Clinical exam	X		X	X	X	X
Blood tests	X		X			
CTA	X ¹			X ²	X ²	X ²
Angiography		X				

¹The CTA must be obtained as close as possible to the study procedure.

²MR or non-contrast CT imaging may be used for those patients experiencing renal failure or who are otherwise unable to undergo contrast-enhanced CT scan, with TEE being an additional option in the event of suboptimal MR imaging.

³Performed yearly for 5 years.

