5.2 Endpoints

The primary safety endpoint will be all-cause and aortic-injury-related mortality at 30 days.

The primary effectiveness endpoint will be device success, defined as technical success (i.e., successful access of the injury site and deployment of the Zenith® TX2® Low Profile Endovascular Graft in the intended location, and endovascular graft patency upon completion of deployment) with none of the following at 30 days:

- Device collapse;
- Type I or type III endoleak requiring reintervention; or
- Conversion to open surgical repair.

The secondary endpoints include an assessment of the following:

- At the intra-operative and post-procedure time points:
 - Procedural time and clinical utility measures (see Appendix C, Definitions);
- Through the 5-year time point:
 - Major adverse events (see Appendix C, Definitions),
 - Injury healing (as determined by maximum transverse diameter at the site of injury),
 - Secondary interventions,
 - Endoleak,
 - Device migration,
 - Device patency,
 - Device integrity, and
 - Device collapse.

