7.4 Missing Data

Missing data will be addressed using three primary strategies: 1) estimating missing data with the best available data, 2) case deletion, and 3) multiple imputation.

The first strategy may be used for missing imaging data. Previous clinical trial experience suggests that some portion of the imaging data may not meet the criteria for accurate measurements by the core laboratory. However, it is recognized that the investigator uses

this information to provide the best possible care for the patient. Therefore, it is reasonable to substitute any missing core laboratory measurements with the corresponding measurements made by the investigator (or his/her staff). In addition, the absence or presence of clinical sequelae may provide the required missing core laboratory assessment of device performance. Furthermore, imaging at subsequent time points may be available, making it possible to infer patient status at the time point of interest. This strategy is a best approximation of the missing data value.

The second strategy is case deletion. If the amount of missing data does not result in a reduction of analyzable patients to a number that is below that required for sufficient statistical power of the primary endpoints, then case deletion will be the method of choice for that analysis.

The third strategy is multiple imputation. This method will be used to predict missing endpoint data. For missing primary endpoint data, the multiple imputation technique will be used to generate random Bernoulli observations with probabilities equivalent to the proportion of (non-missing) “Yes”/ “No” entries. It is anticipated that no covariates will be used for this model. This model-based imputation exercise may provide estimates of the missing data that can be utilized in estimating event rates and confidence bounds. Strategies originating from Schafer¹⁵ will be used, supplemented with notes provided by Schafer.¹⁶ The computations will be performed using PROC MI and PROC MIANALYZE in SAS version 9.1 or later. Unless evidence suggests otherwise, missing at random data will be assumed.

Additional analyses of missing data may be performed as appropriate, including a tipping point analysis.

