APPENDIX C
Definitions

Definitions

Aortic-injury-related

Mortality:	Any death determined by the independent clinical events committee to be causally related to the initial implant procedure, secondary intervention, or rupture of the transected aorta.
Barb Separation:	Radiographic evidence of detachment of barbs from the stent strut.
Calcification:	Fixation zone and iliac artery calcification will be graded based upon the following: None: Lack of calcification; Mild: Less than 40% circumferential calcification; Moderate: 40-70% circumferential calcification; Severe: Greater than 70% circumferential calcification; or Prohibitive: Severe and cannot be resolved in the opinion of the investigator.
Clinical Utility Measures:	Number of ventilator days; days to resumption of oral fluids; days to resumption of normal diet; days to resumption of normal bowel function; duration of ICU stay; days to discharge.
Device Infolding:	Infolding upon deployment due to anatomic constraint (i.e., device oversizing). ⁵
Device Compression/ Collapse:	Failure of the device to maintain its intended expanded diameter after implantation as a result of the dynamic application of external forces (i.e., blood flow). ⁵
Type I Endoleak:	A peri-prosthetic leak occurring at the proximal and/or distal fixation zones.

Type II Endoleak:	A leak caused by retrograde flow from patent vessels. Type IIa includes significant subclavian, celiac, or anomalous vertebral arteries. Type IIb includes bronchial and intercostal artery involvement or minor leaks.
Type III Endoleak:	A leak caused by a defect in the graft fabric, or inadequate seal between modular components.
Type IV Endoleak:	A leak caused by graft fabric porosity, often resulting in a generalized blush of contrast into the injury.
Unknown Endoleak:	Continuing blood flow into the injury with undefined origin.
Injury Severity Score:	The Injury Severity Score (ISS) is an anatomical scoring system that provides an overall score for patients with multiple injuries. Each injury is assigned an Abbreviated Injury Scale (AIS) score and is allocated to one of six body regions (head, face, chest, abdomen, extremities (including pelvis), external). Only the highest AIS score in each body region is used. The 3 most severely injured body regions have their scores squared and added together to produce the ISS score.

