Stroke:	Permanent clinically significant central nervous system deficit.
Success, Device (30-day):	Technical success, with none of the following at 30 days: 
• Device collapse;• Type I or type III endoleak requiring reintervention; or• Conversion to open surgical repair.
Success, Technical:	Successful access of the injury site and deployment of the Zenith® TX2® Low Profile Endovascular Graft in the intended location. The endovascular graft must be patent at the time of deployment completion as evidenced by angiographic imaging.

- Tortuosity: Fixation zone and iliac artery tortuosity will be graded based upon the following:
None: Lack of tortuosity;
Mild: Fairly straight arteries;
Moderate: Angulation manageable with stiff wires, < 70 degrees;
Severe: Angulation difficult, may require surgical exposure for straightening, not straightened entirely with wires; or
Prohibitive: Severe and cannot be resolved in the opinion of the investigator.
- Traumatic Aortic Injury: Injury will be graded based upon the following^{8,17}:
Grade 1: Intimal tear;
Grade 2: Intramural hematoma/large intimal flap (LIF);
Grade 3: Pseudoaneurysm; or
Grade 4: Rupture.

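### A non-contrast CT may stand alone from day 30, and section 7.4 lets absence of symptoms replace the missing reading, so endoleak can be scored absent without having been looked for

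*Combined protocol and SAP*

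**What the plan says.** Table 2 in section 6.9 schedules CTA before the procedure, at 30 days, at 6 months, and yearly from 12 months to 5 years. Angiography is scheduled only intra-operatively, and no CTA is scheduled at the post-procedure visit. Footnote 2 says that MR or "non-contrast CT imaging may be used for those patients experiencing renal failure"; the exception also covers patients otherwise unable to have contrast-enhanced CT. The only back-up is attached to MR, "with TEE being an additional option in the event of suboptimal MR imaging", and not to the non-contrast CT.

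Section 5.2 defines 30-day device success as technical success without device collapse, conversion to open repair, or "Type I or type III endoleak requiring reintervention". Patency enters this endpoint through technical success, for which Appendix C states: "The endovascular graft must be patent at the time of deployment completion as evidenced by angiographic imaging". Endoleak and device patency through 5 years are secondary endpoints.

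Appendix C describes several leak types by flow or contrast; an endoleak of unknown type, for example, is "Continuing blood flow into the injury with undefined origin". Types I and III are defined by the site or cause of the leak. Follow-up patency has no definition there.

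On missing imaging, section 7.4 says that "the absence or presence of clinical sequelae may provide the required missing core laboratory assessment of device performance". The same section also offers the investigator's measurements, later imaging, case deletion and multiple imputation, with tipping-point analysis as an option.

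**The concern.** Endoleak and patency concern flow. An unenhanced CT does not show flow in the lumen; this is general imaging knowledge, and the documents do not state it. A patient followed under footnote 2 by non-contrast CT alone may thus have no flow image after the completion angiogram, and possibly none through 5 years.

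Core-laboratory reading does not close the gap. If the laboratory marks endoleak as not assessable, section 7.4 allows a lack of clinical sequelae to take the place of the reading. A finding that could not be seen then becomes a finding recorded as absent.

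The study is single-arm and descriptive, so the reported rates are the result. Section 7.5 expects them to serve as prior information for later device variations, which would carry any optimism forward. Section 5.4 promises uniform definitions and an analysis plan fixed in advance, yet for these patients the plan leaves open which of several treatments of the missing item applies.

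**Working it through.** **The plan's own figure.** The sample size in section 7.1 is for 30-day mortality: n = 1.96² × 0.076 × 0.924 / 0.08² = 42.15, rounded up to 43, with 50 to be enrolled. It reproduces and does not depend on imaging. The plan gives no expected value for device success or for endoleak.

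**Which components are exposed.**

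- *Patency within device success:* judged on the completion angiogram. Not exposed.
- *Device collapse:* defined as "Failure of the device to maintain its intended expanded diameter after implantation", a matter of shape. Not dependent on contrast.
- *Conversion to open repair:* a clinical event. Not exposed.
- *Type I or III leak requiring reintervention:* exposed. Section 6.7 says "Type I and type III endoleaks warrant immediate treatment", so detection leads to reintervention. A leak that nobody sees prompts none, and the patient counts as a success.
- *Secondary endoleak (all types) and follow-up patency:* exposed.

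For each exposed item the error is either zero or in the device's favour.

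**Size for 30-day device success.** Let N = 50, let k be the number of patients whose 30-day image is a non-contrast CT only and who are scored leak-free, and let q be their true risk of an unseen type I or III leak that would have required reintervention.

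Bias in percentage points = 100 × (k / N) × q

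The documents give neither k nor q. The ranges below are assumptions.

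| k | q = 2% | q = 20% | Ceiling (every such patient has a missed leak) |
|---|---|---|---|
| 0 | 0 | 0 | 0 |
| 1 | 0.04 | 0.4 | 2 |
| 3 | 0.12 | 1.2 | 6 |
| 5 | 0.2 | 2.0 | 10 |
| 10 | 0.4 | 4.0 | 20 |

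One actual hidden failure moves the rate by 1/50 = 2 points.

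**Size for the secondary endoleak rate.** If 3 to 8 of 50 patients were imaged this way and 10% to 30% of them had a leak of any type (again assumptions), 0.3 to 2.4 leaks would go unseen, or 0.6 to 4.8 points.

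**What the choice of handling does.** Suppose 48 of 50 patients are scored as successes and three of the 48 could not be read for leak:

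- kept as successes: 48/50 = 96.0%
- excluded: 45/47 = 95.7%
- counted as failures: 45/50 = 90.0%

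Exclusion hardly moves the figure. Only the last line shows how much rests on patients who were not examined.

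**The case against.** The best reply is that section 7.4 permits this substitution but does not prescribe it. Investigator measurements and later imaging are also available, case deletion is the preferred method while enough analysable patients remain, and imputation and a tipping-point analysis are provided for. The exception reaches only patients who cannot have contrast CT, and MR is an equal alternative within it. All endpoints are descriptive, so no test decision can change.

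All of this stands, and it limits the point to what can happen. It does not remove the point: the substitution from clinical sequelae sits in the strategy aimed at imaging data, nothing rules it out for endoleak or patency, and nothing says which strategy takes precedence in this situation.

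Three stronger readings are tempting, and the documents support none of them:

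- *That the device-success rate is too high.* Neither the number of patients on this route nor their risk of a missed leak is given, so the documents support only that it could be.
- *That unseen patency problems at 30 days inflate device success.* That component is settled by angiography at the end of deployment.
- *That the 0.6 to 4.8 points apply to device success.* They concern leaks of any type. A missed type II, type IV or unknown leak, or a type I or III leak not requiring reintervention, cannot change the primary endpoint.

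**Conclusion.** The gap is real and its direction is known; its size is not. Footnote 2 and section 7.4 together allow a patient without flow imaging after the completion angiogram to be scored free of endoleak and patent at follow-up. The secondary endoleak and patency rates can be biased in the device's favour. So can 30-day device success, but only through an undetected type I or III leak that would have required reintervention.

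Each such hidden failure is worth 2 points at N = 50. In expectation, for 1 to 5 affected patients and an assumed risk of 2% to 20%, the bias in device success is about 0.04 to 2 points. It is zero if no patient takes this route or none on it has a missed leak. The conclusion rests on those assumed ranges and on the general premise that a non-contrast CT cannot show flow. It is worth correcting because the reported rate is the study's main product and the correction is cheap.

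**What to change.** In sections 5.2 and 7.4, add a scoring rule:

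- Absence of endoleak and patency at follow-up are scored only from flow-capable imaging (CTA, contrast MR, TEE or angiography) at that visit or a later one.
- Absence of clinical sequelae alone may not fill either item.
- A non-contrast CT is non-evaluable for these two items but still usable for collapse, diameter, migration and fracture.

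In the report, give the number of patients affected at each visit and a separate denominator for each component. Because leaving the leak component missing does not settle how the composite is scored, present 30-day device success three ways: as scored, with these patients excluded, and with them counted as failures. Cross-refer footnote 2 to this rule so that the imaging table and the endpoint definitions agree.

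The rule concerns scoring only. It calls for no additional scan and does not alter which scan a patient has. The cost is a few sentences, a few more missing values, and a success figure that may be slightly less favourable or shown with a wider range.
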